6.7.3.2 Assessment of Chronic/Recurrent Symptoms

GI symptoms were the most common potentially allergic symptoms to occur on a subacute, chronic, and/or recurrent basis during Phase 2 clinical trials with AR101. Atopic dermatitis, seasonal allergies, or asthma are other potentially non-acute allergic reactions that could be brought on or exacerbated by OIT. The absence of a clear temporal relationship between dosing and the emergence of recurrent symptoms may help to distinguish these from acute dosing-related symptoms.

If symptoms arise that suggest a chronic/recurrent reaction to IP, the dose level should be reduced. As with acute symptoms, the level of the dose reduction should be guided by the severity of the symptoms. Symptomatic treatment is permitted ([Section 5.9](#)), but should be used as a supplement to dose reduction, not a substitute for it.

For chronic/recurrent GI symptoms, especially upper GI symptoms, investigators are advised to have a low threshold for instituting a dose reduction and/or for considering early discontinuation of affected subjects from the study, owing to the potential for EoE.

For subjects determined to be having dose-limiting chronic/recurrent GI symptoms up to and including the 20 mg/d dose level, it is advised that dosing of IP be suspended for 4 weeks and resumed at a dose level of 3 mg/day for a minimum of 4 weeks, with the first dose given in the CRC under medical supervision. If tolerated, up-dosing may resume, with caution, according to the usual schedule, as tolerated. (Note: the 4-week suspension of dosing in response to chronic/ recurrent GI symptoms occurring up to and including the 20 mg/d level is the only protocol-specified exception to the rules for missed OIT delineated in [Section 6.8](#).)

For subjects who develop dose-limiting chronic/recurrent GI symptoms at the 40 mg/d dose level or above, dose reduction and re-escalation is to proceed as described in [Section 6.3.3](#).

6.7.4 Treatment of Acute Reactions to Peanut OIT During Initial Escalation

[figure not shown]
The process algorithm for responding to acute allergic symptoms during OIT is shown in [Figure 2](#). Explanatory text follows the figure.

Investigator judgment will be required to determine the best course of action. An Aimmune medical monitor will be available at all times to answer any questions or to assist in any decisions related to the study protocol. Possible actions are listed below:

- Extending the time interval between dosing (up to an additional 30 minutes) without any additional treatment
- Instituting enhanced clinical monitoring. This could include (though is not limited to) more frequent vital sign monitoring (including respiratory rate), auscultation, and/or the addition of pulse oximetry
- Treating with antihistamine and then resuming dose escalation within 60 minutes of last dose, if assessed as safe

- Treating additionally with epinephrine, beta-agonist, oxygen, IV fluids, and/or glucocorticosteroids, as necessary, and discontinuing dose-escalation
- Discontinuation of desensitization protocol

Figure 2 Schematic for Management of Symptoms Occurring During Initial Escalation Day 1

- **Oral/pharyngeal pruritus/Mild symptoms:** For *oral/pharyngeal pruritus* occurring in isolation, a specific type and commonly occurring mild allergic reaction, the recommended action is to advance to the next dose in 30 minutes (though the action taken is, as always, at the investigator's discretion).

For other *mild symptoms*, the action to be taken, at the investigator's discretion, should be to either:

- Advance to next dose in 30 to 60 minutes, *or*
- Treat with antihistamine and then resume dose escalation within 60 minutes of the last dose, provided that symptoms have resolved to the point where the investigator assesses the subject to be safe to continue dosing (ie, having no or only minimal residual signs or symptoms)

In general, if a subject requires only 1 or 2 doses of antihistamine to treat mild symptoms occurring during the course of the initial escalation, then the initial escalation may continue. If, however, the subject requires a second medication (eg, epinephrine or a beta-agonist) to treat the symptoms, or more than 2 doses of an antihistamine, the initial escalation is to be terminated and the subject is to receive no further OIT, even if the symptoms were assessed to be mild. Use of epinephrine to treat dose-related symptoms, even in the unlikely event that the symptoms are graded as mild, will be cause to terminate the initial escalation.

Moderate symptoms: For moderate symptoms, if the symptoms are not worsening or amassing at a rapid pace, then a stepwise approach to treatment may be taken at the discretion of the investigator. If the first action undertaken is to implement an observation period, the observation period should not exceed 30 minutes before either the symptoms are noted to be resolving or therapy is instituted. Whether treatment is initiated immediately or after an observation period, the subject may be treated first with antihistamines or immediately with epinephrine, as deemed appropriate by the investigator. Other therapies may be added either sequentially or simultaneously, per investigator judgment.

If moderate symptoms occur at any of the doses below 6 mg (ie, up to and including 3 mg), then the desensitization procedure will be discontinued. The decision to discontinue escalation is to be based solely on the determination of whether the allergic reaction was of moderate severity. Although it is generally the case that some form of treatment will be instituted for moderate symptoms, treatment is not a requirement for assessing an allergic reaction as being of moderate severity.

Severe symptoms: For severe symptoms, the actions taken should be to discontinue the initial escalation and administer the appropriate rescue medications. The desensitization procedure will be discontinued regardless of the dose at which the severe symptom or symptoms occurred.

The medical monitor will answer any questions and assist in any decisions related to the study protocol.

6.7.5 Treatment for Reactions During the Up-dosing Period: Dose Adjustment

If a dose or dose level is assessed as *not tolerated*, the action taken will depend on the type and severity of the dose-related reaction and the investigator's clinical judgment. The following possible actions are at the investigator's disposal and are considered in greater detail in subsequent sections ([Section 6.7.5.1](#), [Section 6.7.5.2](#), and [Section 6.7.5.3](#)):

- Dosing the subject under medical supervision in the CRC – this is encouraged whenever there is question as to the tolerability of a dose level. It may be performed at the current dose level or at a reduced dose level if there is already a high index of suspicion that the current dose level has not been tolerated.
- Holding dose level at current level for an additional 1 to 2 weeks before attempting dose escalation – this may be done at the discretion of the investigator if there is concern that the current dose level has not been sufficiently well tolerated to attempt up-doing to the next dose level.

[figure not shown]
- Reducing dose by 1 or 2 dose levels and maintaining the reduced dose level for at least 1 to 2 weeks before attempting dose re-escalation – Generally, this should be the action taken when a dose that has been observed in the CRC is assessed as not tolerated, if a dose elicits moderately severe symptoms, or if the investigator is convinced of the intolerance of the current dose level. In short, it should be considered the default action whenever a dose or dose level is assessed as *not tolerated*.
- Reducing dose level for less than the usual 2-week period – this may be instituted as treatment for an intercurrent AE, to aid the investigator in determining if a dose level is or is not tolerated, or if a pattern of decreased IP tolerability during menses is discerned. The level of the reduction in dose, ranging from a 1-step reduction to a 50% reduction will be at the investigator's discretion, based on clinical judgment. The manner in which dose escalation may resume will depend on the level and the duration of the dose reduction.
- Temporarily withholding IP dosing – this may be instituted as treatment for an intercurrent AE or to aid the investigator in determining if a dose level is or is not tolerated, but the duration of withholding IP may not exceed 14 consecutive days, or the subject will be discontinued from the study. The manner in which dosing may resume after withholding dosing of IP depends on the duration for which dosing was withheld.
- Reducing dose by 1 or 2 dose levels and maintaining the reduced dose level for a duration of time recommended by the investigator – this is instituted if epinephrine is given to treat a dose-related allergic reaction. The dose reduction is per investigator discretion based on the type and severity of symptoms ([Section 6.7.6](#)).
- Stopping dosing and discontinuing the subject early from the study – this is an option that the subject may elect at any time and for any reason. The investigator must discontinue the subject from further dosing and continuation in the trial under circumstances that could jeopardize the health of the subject or the integrity of the trial.

6.7.5.1 Reactions During the Up-dosing Period

If symptoms arise in the clinic after up-dosing, the investigator is to determine whether or not the dose was tolerated (Section 6.7.3). The process algorithm for continued dosing after dose-related symptoms occur is depicted in Figure 3. Explanatory text follows the figure.

Dose adjustment after administration of antihistamines and/or epinephrine for dose-related allergy symptoms is described in Section 6.7.6.

Figure 3: Schematic for Up-dosing Period Dose Adjustment

- **No symptoms:** If a subject has a dose escalation in the CRC without symptoms, the action should be to continue, per protocol, with daily home dosing at the tolerated dose level and return to the CRC for the next scheduled dose escalation visit 2 weeks later.
- **Oral/pharyngeal pruritus:** If a subject experiences *oral/pharyngeal pruritus* following the administration of the first dose at a new dose level, the dose will generally be *assessed as tolerated*, and the same dose can be repeated the next day at home and continued throughout the 2-week home-dosing interval, unless other symptoms begin to develop.
- **Oral/pharyngeal pruritus:** If only *oral/pharyngeal pruritus* occurs following the administration of the first dose at a new dose level, the dose will generally be *assessed as tolerated*, and the same dose can be repeated the next day at home and continued throughout the 2-week home-dosing interval, unless other symptoms begin to develop.

- **Mild symptoms assessed as tolerated:** If *mild symptoms* occur with the first dose at a new dose level and the dose is *assessed as tolerated*, the action taken should be to repeat the same dose the next day. It is advised that the repeat (next day's) dose be administered in the CRC, but it may be given at home, at the investigating physician's discretion. If the second dose at the new (increased) dose level is tolerated without symptoms, then the subject is to continue on that dose level for the requisite 2 weeks and return to the CRC for up-dosing at the next scheduled visit. If the dose again causes mild symptoms, but is *assessed as tolerated*, the subject may continue at that dose level or return to the last tolerated dose (at the investigator's discretion) and continue dosing at home for the next 2 weeks at the investigator-determined dose level. ([Section 6.7.5.2](#) for actions to be taken in the event that symptoms develop during home-dosing.) If, following the first dose at a new dose level, the second dose at the new (increased) dose level is again accompanied by mild symptoms, but is *assessed as not tolerated*, the procedures outlined in the paragraph above should be followed.
- **Mild symptoms indicating uncertainty regarding tolerability:** If other mild symptoms occur that indicate uncertainty regarding tolerability, the investigator will determine whether the subject should receive the next dose in the CRC or at home. If the investigator determines that the subject requires medical supervision to determine tolerability, the subject will receive the next dose at the CRC. If the investigator determines that the subject does not need medical supervision, the procedure will be to split the home dose into 2 doses taken 8 to 12 hours apart OR hold the current dose level for an addition 1 to 2 weeks OR reduce the dose by 1 or 2 dose levels and maintain the reduced dose for at least 1 to 2 weeks before attempting dose re-escalation.
- **Mild symptoms assessed as not tolerated:** If other *mild symptoms* occur with the first dose at a new dose level and the dose is *assessed as not tolerated*, the action taken should be to have the subject return to the CRC the next day for dosing at the last tolerated dose (ie, a 1-step dose reduction) under medical supervision (if the subject is unable to return to the CRC on the day specified, the investigator may initiate an approximate 1 dose-level reduction at home, with the subject coming to the CRC at the earliest date possible). If the reduced dose is *assessed as tolerated*, the subject is to continue on that daily home dose for at least 1 to 2 weeks. ([Section 6.7.5.2](#) for actions to be taken in the event that symptoms develop during home-dosing.) If the reduced dose is again *assessed as not tolerated*, the subject is to return to the CRC the next day for supervised dosing at a 1- or 2-step reduction in dose (per investigator judgment, based on severity of reaction). If this further reduced dose is *assessed as tolerated*, the subject will continue at that dose level for daily home-dosing over the ensuing 2 weeks. If, however, the reduced dose is *assessed as not tolerated*, the subject is to be considered an escalation failure non-responder.
- **Moderate symptoms:** If *moderate symptoms* occur with the first dose at a new dose level, except for rare instances, the dose will be *assessed as not tolerated*. The action taken should be to have the subject return to the CRC the next day for dosing at the last tolerated dose under medical supervision. If this reduced dose elicits no allergic symptoms (ie, is well tolerated), the subject will continue on that daily home dose

level for an additional 2 weeks. If the subject experiences mild symptoms at the reduced dose, the procedures for responding to a dose with mild symptoms should be followed (above and [Figure 3](#)). If the subject experiences moderate symptoms at the reduced dose level, the subject should return to the CRC the next day and receive a further 1- or 2-step dose reduction (per investigator judgment). If this reduced dose is well tolerated, it will be continued as the daily home dose for at least 2 weeks before re-escalation is attempted in the CRC. If the dose is not well tolerated, but elicits mild symptoms, then the treatment procedures for responding to mild symptoms should be followed (above and [Figure 3](#)). If, however, the subject again experiences moderate symptoms at the reduced dose level, a discussion with the medical monitor is to ensue to reach a decision as to whether to continue the subject in the study.

In the rare instance that a dose eliciting moderate symptom is *assessed as tolerated*, then the actions taken should be the same as for a dose with mild symptoms *assessed as tolerated*.

- **Severe symptoms:** If *severe symptoms* occur, the action should be to treat the subject for the allergic reaction, and then, in consultation with the medical monitor, decide whether or not to discontinue the subject from the study. If it is determined that it is safe to allow the subject to continue in the study, the subject should return to the CRC the next day for dosing at a 2-step reduction in dose under observation. If the subject tolerates the dose reduction (ie, shows no or only mild symptoms that are assessed as tolerated), then the subject is to remain at the reduced dose level for at least 2 weeks before returning to the CRC to attempt dose re-escalation. If the subject does not tolerate the reduced dose, then the subject is to be considered an escalation failure non-responder.

Consult the medical monitor for specific questions related to dose escalation or continuation of the same dose that are not answered in the procedures described above.

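### Protocol Section 6.7.5.1 sends a repeat dose assessed as not tolerated to a paragraph above that deals only with tolerated doses, in conflict with Section 6.7.5 and a later bullet

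*Protocol*

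**What the plan says.** Protocol Section 6.7.5.1 lists what to do when symptoms follow an up-dose in the clinic, by type and severity of symptom. The bullet on mild symptoms assessed as tolerated has the same dose repeated the next day, in the clinic or at home. It closes with the case where "the second dose at the new (increased) dose level is again accompanied by mild symptoms, but is" judged not tolerated. For that case the whole instruction is that "the procedures outlined in the paragraph above should be followed". The sentence gives no section number, bullet heading or figure.

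Three other places bear on it:

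- **Directly above, in Section 6.7.5.1.** The oral/pharyngeal pruritus bullet appears twice in nearly the same words. After a first dose at a new level, the dose will generally be judged tolerated. The bullet then allows this: "the same dose can be repeated the next day at home and continued throughout the 2-week home-dosing interval, unless other symptoms begin to develop".
- **Two bullets below, in Section 6.7.5.1.** Where a first dose causes mild symptoms and the investigator finds that it was not tolerated, the instruction reads: "the action taken should be to have the subject return to the CRC the next day for dosing at the last tolerated dose". That dosing is to be supervised.
- **The parent Section 6.7.5.** On reducing by 1 or 2 dose levels: "it should be considered the default action whenever a dose or dose level is assessed as" not tolerated.

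**The concern.** The sentence is an operative dosing instruction for children on an allergen. It is also the only sentence among the Section 6.7.5.1 bullets that addresses a repeat dose at the new level assessed as not tolerated. If it points to the wrong place, the investigator must work out which rule applies. One site may follow the pointer upward, a second may take the lower bullet although it speaks of the first dose, and a third may fall back on the general default in Section 6.7.5. The same event could then lead to different dosing at different sites.

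Safety handling is the main stake. There is also a more distant statistical one. The lower bullet can end in the subject being called an escalation failure non-responder, and Section 9.2.1 counts such subjects as treatment failures for the primary endpoint.

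**Working it through.** No arithmetic applies. The check is where the pointer lands and whether the rule found there fits the case.

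**1. Order of the bullets in Section 6.7.5.1**

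1. No symptoms
2. Oral/pharyngeal pruritus
3. Oral/pharyngeal pruritus (second printing)
4. Mild symptoms assessed as tolerated; the pointer is its last sentence
5. Mild symptoms, tolerability uncertain
6. Mild symptoms assessed as not tolerated
7. Moderate symptoms
8. Severe symptoms

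The pointer in item 4 looks upward, to items 1 to 3. Those cover a dose without symptoms or a dose generally judged tolerated, with dosing continued at home. None covers a dose that was not tolerated. The bullet with that subject is item 6, below the pointer.

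**2. The candidate rules side by side, for a repeat dose assessed as not tolerated**

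| Source | Condition in its own text | Action |
|---|---|---|
| Item 3, directly above | Pruritus after the first dose at a new level, generally judged tolerated | Same dose may be repeated at home |
| Item 6, below | Other mild symptoms with the first dose at a new level, not tolerated | Supervised dosing in the clinic next day at the last tolerated dose |
| Section 6.7.5 | Any dose or dose level assessed as not tolerated | Reduction by 1 or 2 levels as the default |

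The first row cannot stand with the other two for the same event. Neither item 3 nor item 6 matches the case by its own words, since both speak of the first dose.

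**3. Other routes.** Item 4 lets the repeat dose be given at home. For home doses not tolerated, Section 6.7.5.2 refers to Section 6.3.3, and Section 6.3.3.1 refers back to Section 6.7.5 for setting the lower dose. That chain leads to reduction, but indirectly, and the sentence at issue does not mention it.

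**4. Conditions for the case to arise.** All of these are needed: mild symptoms with the first dose at a new level; that dose assessed as tolerated; mild symptoms again with the repeat dose; and the repeat dose assessed as not tolerated. Section 6.3.3 schedules 10 Up-dosing Visits, so there are several occasions per subject. The protocol gives no rate for any of the conditions, so no frequency follows.

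**5. Distance to the primary endpoint under item 6.** After the triggering dose, the last tolerated dose must also be not tolerated (first further failure), and then a further 1- or 2-step reduction must be not tolerated (second further failure). Only then is the subject an escalation failure non-responder.

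**The case against.** The strongest reply is that this is a stray cross-reference which a competent investigator would see through. The pruritus bullet is limited to pruritus after a first dose, uses permissive wording, and stops applying once other symptoms develop. A repeat dose already recorded as not tolerated falls outside it. A bullet in the same list carries the matching heading, Section 6.7.5 states a general default, and Section 6.7.5.1 ends by sending unanswered questions to the medical monitor. Figure 3, the algorithm that the bullets explain, is not shown in the copy reviewed and may settle the case.

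Much of this stands, and it rules out some stronger readings:

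- A reader might infer that the protocol orders a child who has failed a second dose to keep taking it at home for 2 weeks. It does not; the conditions and permissive wording of the pruritus bullet do not support that.
- A reader might infer that one further failure makes the subject a primary-endpoint failure. The lower bullet requires two.
- A reader might infer that any subject with mild symptoms on a first dose is exposed. All the conditions above must be met, and Section 6.7.2 expects most mild reactions to meet the criteria for a tolerated dose.
- A reader might infer that Maintenance is equally affected. Section 6.7.7 does carry the guidelines over, but the trigger is a new, increased dose level, which in Maintenance arises mainly on re-escalation after a reduction.

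The reply does not remove the defect. The sentence cites a paragraph, not the figure. The lower bullet is worded for the first dose, so its heading alone does not cover the repeat dose. The medical monitor is offered for questions left unanswered, whereas here the text appears to give an answer.

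**Conclusion.** The pointer is wrong as written. Nothing above it in Section 6.7.5.1 deals with a dose that was not tolerated, and following it literally conflicts with both Section 6.7.5 and the later bullet in the same list. Handling could therefore differ between sites for the same event. The consequence is direct for safety and remote for endpoint classification.

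The size cannot be put in numbers, and the set of conditions is narrow. The conclusion rests on the order of the bullets as printed and on the text alone. If Figure 3 gives a clear path for this case, the practical effect is smaller, but text and figure would then still need to be brought into line. It should be corrected because it is a live dosing instruction and the correction is nearly free. Which rule should apply is for the sponsor to decide.

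**What to change.** Reconcile Section 6.7.5 with the pruritus bullets, the bullet on mild tolerated symptoms and the bullet on mild not-tolerated symptoms in Section 6.7.5.1:

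- Replace the reference to the paragraph above with the heading of the rule that the sponsor intends.
- Make that rule say that it covers the repeat dose at a new level as well as the first.
- Delete one of the two oral/pharyngeal pruritus bullets.
- Check that Figure 3 shows the same path.

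The cost is one cross-reference, a few words of scope, one deletion and a check of the figure. Sample size and analysis are unaffected, and no dose or clinical rule is proposed here.

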- Any subject deemed to have **severe symptoms** that include hypoxia, hypotension, or change in mental status (stage 3 anaphylaxis defined in [Appendix 3](#)), or who receives intensive therapy (to be determined by the investigator, but may include such interventions as IV epinephrine, intubation, or admission to an intensive care unit) for an allergic reaction at any time should be discussed with the medical monitor and discontinued from the study.
- On the day following in-clinic up-dosing, the site is to make telephone contact with the subject/subject's parent or guardian to enquire if any AEs (including allergic symptoms) occurred subsequent to the subject leaving the clinic, and to provide assistance in the recording of any such events in the diary.
- A dose escalation attempt may be postponed 1 to 2 weeks if, in the clinical judgment of the investigator, the current dose level has not been sufficiently well tolerated to proceed to the next dose level.
- If an investigator suspects that a subject has not tolerated, or is not tolerating, his or her current dose level, the investigator should have the subject return to the clinic to determine whether a dose reduction is warranted, and if so, the magnitude of the reduction. The investigator may also decide to maintain the current dose or to withhold dosing. Guidelines for setting the new, lower dose are outlined in [Section 6.7.5](#), with the dose adjustment depending on the severity of the dose-related symptoms.
- Subjects who require dose reduction during a 2-week dosing period will have their escalation schedule reset, as necessary, to maintain the new dose level for a 2-week period prior to attempting to re-escalate.
- Following a dose reduction, it is advised that an escalation attempt be made by 4 weeks, unless escalation is to be delayed further due to administration of epinephrine, as defined in [Section 6.7](#). Failure to successfully escalate after 3 consecutive attempts, with each attempt spaced at least 2 weeks apart, will result in the cessation of dosing. The subject will be asked to return to the CRC 14 to 16 days following the last dose of IP to undergo an Early Discontinuation Visit ([Section 6.4](#)) and is to be followed for safety in the interim.
- For symptoms occurring during the Maintenance Period, the same study dosing rules and guidelines that apply for the Up-dosing Period will also apply.

6.3.3.2 80 mg Up-dosing Visit

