7.11.2 Individual Stopping Rules

Individuals may stop the study at any time if they experience subjectively intolerable AEs or dosing symptoms. They must halt up-dosing and re-start with a reduced dose if more than 3 days of dosing are missed. Seven or more consecutive days of missed dosing due to non-compliance constitutes an individual stopping rule, as does a significant number of episodes of missed dosing (ie, 3 or more consecutive days on at least 3 occasions) during the Up-dosing Period. Missing 15 or more consecutive days of dosing for any reason also constitutes an individual stopping rule. [Section 4.3.1](#) provides additional individual stopping rules.

Occurrence of any of the following will result in the cessation of dosing:

- Failure to accomplish up-dosing of IP after 3 attempts
- Failure to identify a tolerated dose of IP after 3 attempts at dose reduction
- Administration of 3 or more doses of epinephrine for the treatment of any dose-related allergic reaction.

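### The Up-dosing stopping rules for repeated intolerance are inconsistent: repeated mild reactions have a stricter rule than moderate ones, and Section 7.11.2 states a different count

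*Protocol*

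**What the plan says.** Section 6.7.5.1 sorts reactions to the first dose at a new level by severity.

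- **Mild, not tolerated.** The subject is dosed the next day at the last tolerated level. If that fails, "the subject is to return to the CRC the next day for supervised dosing at a 1- or 2-step reduction in dose". If that also fails, "the subject is to be considered an escalation failure non-responder".
- **Moderate.** The subject goes through the same two reductions. "If, however, the subject again experiences moderate symptoms at the reduced dose level, a discussion with the medical monitor is to ensue" on whether the subject stays in the study. If the second reduced dose produces only mild symptoms, the text refers the site to the procedures for mild symptoms.
- **Severe.** The medical monitor is consulted first. A subject who continues is dosed two steps lower. "If the subject does not tolerate the reduced dose, then the subject is to be considered an escalation failure non-responder".

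Section 7.11.2 lists events that end dosing, without reference to severity. Two of them are "Failure to identify a tolerated dose of IP after 3 attempts at dose reduction" and "Failure to accomplish up-dosing of IP after 3 attempts".

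Section 6.3.3.1 words the escalation rule differently: "Failure to successfully escalate after 3 consecutive attempts, with each attempt spaced at least 2 weeks apart".

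Section 9.2.1 counts escalation failures, and subjects who stop OIT before the Exit DBPCFC, as failures for the primary endpoint. Sections 6.3.3.1 and 6.7.7 apply the Up-dosing rules to the Maintenance Period as well.

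**The concern.** These rules decide whether a child with no identified tolerated dose goes on receiving allergen. They should give one answer wherever a site looks, and the answers should follow an order that a reader can understand. As written, repeated mild reactions end treatment automatically at a point where repeated moderate reactions leave room for judgement, and no reason is given. A third count appears in another section without explanation.

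There is also a link to the efficacy result. A stopped subject is a non-responder by definition, while a subject who continues still has a chance of response. The rules are likely to apply mostly in the AR101 arm: in ARC001, treatment-emergent hypersensitivity events occurred in 90% of AR101 subjects and 50% of placebo subjects (Section 1.2.1).

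**Working it through.** This is mainly a comparison of texts.

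**1. Count the failed reductions in each rule.** The failed first dose at the new level is not counted.

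| Rule | Failed reductions | Consequence |
|---|---|---|
| Mild, not tolerated (6.7.5.1) | 2 | automatic escalation failure |
| Moderate (6.7.5.1) | 2 | medical monitor discussion; may continue |
| Severe, if allowed to continue (6.7.5.1) | 1 | automatic escalation failure |
| General rule (7.11.2) | 3 | dosing ends |

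The ordering by severity is not monotone. Moderate reactions have the most lenient rule, and mild ones are treated more strictly than moderate ones.

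**2. Apply all the rules together, stopping at the earliest.** For mild reactions the stop comes at min(2, 3) = 2, and for severe reactions at min(1, 3) = 1. For moderate reactions there is a discussion at 2 and, if the subject continues, a stop at 3. Within the acute branches, the three-attempt rule therefore operates only for moderate reactors who have been allowed to continue. It never operates on the mild or severe branch, although it is worded for everyone.

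**3. Follow a subject who changes branch.** Take a moderate reactor whose second reduced dose gives mild symptoms that are assessed as not tolerated. The mild procedures now apply, but the text does not say where the count stands.

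- If the count carries over, two reductions have failed and the subject is an escalation failure at once.
- If the count restarts, the mild branch allows two more, 2 + 2 = 4 in total, unless Section 7.11.2 intervenes at 3.

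The same child can thus be stopped at two, three or four failed reductions, depending on the reading.

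**4. Compare the escalation rules.** Both say three attempts. Section 6.3.3.1 requires them to be consecutive and at least 2 weeks apart; Section 7.11.2 has neither condition. A subject with three failures separated by a success is stopped under the literal text of 7.11.2 but not under 6.3.3.1.

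**5. Size on the primary endpoint.** Section 9.4 plans 120 AR101 subjects. One AR101 subject changing between responder and failure moves the response rate by 1/120 = 0.83 percentage points. That is a ceiling per subject, because continuing does not make a subject a responder.

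For context, exact enumeration of Fisher's test (120 vs 40, two-sided 0.05) gives power of 82.8% at 39% vs 15% and 92.1% at 43% vs 15%. This agrees with the protocol's statements of at least 80% and at least 90%, and the sample size is not in dispute. The documents give no number of affected subjects. Purely as an assumption, if 1, 2, 3, 4 or 6 would-be responders became failures, power at the 39% scenario would be 80.3%, 77.5%, 74.5%, 71.3% or 64.3%. Nothing in the protocol supports any particular value in that range.

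**The case against.** The strongest reply is that nothing here forces a site to break one rule in order to obey another. Section 7.11.2 says that any listed event ends dosing, and it refers to Section 4.3.1 for further stopping rules. Its conditions are sufficient, not exclusive. A reader might infer that dosing stops only after three failed reductions, or that the moderate branch is open-ended. The text supports neither: 7.11.2 does not tell a site to try a third reduction after the mild branch has ended, and it caps the moderate branch at three. The cap can also serve as a backstop for reductions that arise elsewhere, such as for chronic or recurrent symptoms (Section 6.7.3.2). All of this stands.

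A reader might also infer that a moderate reactor who improves to mild symptoms is moved onto a stricter track. That reads too much into the text. Section 6.7.5.1 uses well tolerated to mean free of allergic symptoms, so the referral to the mild procedures also covers mild symptoms assessed as tolerated or uncertain, where continuing, holding, splitting or reducing the dose is allowed. Only mild symptoms judged not tolerated reach the failure step.

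The difference between mild and moderate is an odd ordering rather than a literal contradiction, since each branch has its own instruction. The escalation wording in 7.11.2 may simply be shorthand for 6.3.3.1. Figure 3, which the text explains, is not shown in the copy reviewed, and Section 6.7.5.1 sends unanswered dosing questions to the medical monitor.

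These replies narrow the point but do not remove it. The harmonised reading leaves the inverted ordering unexplained, leaves a rule worded for everyone idle on two of the three acute branches, and leaves the carry-over of counts undefined. Referral to the medical monitor settles cases one at a time, which does not ensure that they are settled alike.

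**Conclusion.** The stopping rules for repeated intolerance are inconsistent as written and should be reconciled. The finding rests on the text alone: two failed reductions and automatic failure for mild reactions, two and a discussion for moderate, one and automatic failure for severe, and three in a general rule that ignores severity. The undefined carry-over between branches is part of the same defect. The escalation wording is a lesser point.

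The effect on the primary endpoint is bounded at 0.8 percentage points per AR101 subject, and its total is unknown. A reader might infer that the primary result is under threat; the documents do not show that. A subject who continues must still reach 300 mg/d by Week 40, hold it for the last 4 weeks without symptomatic therapy and tolerate the 1000 mg challenge. Nor can the 6 of 29 AR101 subjects who withdrew in ARC001 stand in for the number affected, since nothing ties those withdrawals to repeated failed reductions. Early stopping counts as failure, so if it falls mainly on AR101 it works against the drug and does not favour it.

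The main reason to act is that sites should handle the same reaction in the same way for safety. No view is taken on which count or rule is clinically right.

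**What to change.** Reconcile Sections 6.3.3.1, 6.7.5.1 and 7.11.2 into one set of rules that states:

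- for each symptom severity, how many failed reductions and how many failed escalations end dosing;
- whether the count of failed reductions carries over when a subject moves from one severity branch to another;
- whether failed escalation attempts must be consecutive and spaced;
- who decides, where a decision is left open.

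Use the same text in all three sections and check Figure 3 against it. If the difference between the mild and moderate branches is intended, give the reason. The choice of rule belongs to the sponsor's clinicians.

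The cost is a wording change in three sections and a memo to sites. It needs no new procedures or subjects.
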